#### 5.2.1 *Assessment of Compliance*

Dosing instructions will be reviewed and subjects will be interviewed to assess treatment compliance at the following Visits: Weeks 2-5, 7, 9, 11, 13, 17, 21, and 25. Any lapses in treatment compliance will be addressed with the subject during these visits.

### 5.3 OXD01

#### 5.3.1 *Initiation, Training*

The Investigator/designee will receive instruction on initiating and training subjects to use OXD01 (see OXD01 Clinician Guide) prior to enrolling the first subject at the site.

On study Day 1 subjects randomized to SL BUP/NAL plus the OXD01 digital therapeutic will be trained by the Investigator or designee to use OXD01 (see OXD01 Clinician Guide and Patient Guide) and will begin to access the therapeutic counseling modules for 15-30 minutes, 1-2 times per week as instructed. OXD01 training should be conducted as soon as the subject is clinically stable, with physical withdrawal symptoms managed and the

subject able to fully participate in the process, but no greater than 14 days from the first dose of SL BUP/NAL induction. Training should include a discussion of the key concepts of recovery and working with OXD01 (OXD01 Clinician Guide, Getting Subjects Started with MODIA – Training and Registration).

### 5.3.2 *Assessment of Compliance*

Subjects must continue to use OXD01 for 15-30 minutes, 1-2 times per week from Day 1 (Section 5.3.1) through Day 169. Treatment compliance will be assessed through subject interviews at the following Visits: Weeks 2-5, 7, 9, 11, 13, 17, 21, and 25. Lapses in compliance with the recommended use of OXD01 will be addressed with the subject. The Investigator or designee will also record the following OXD01 usage information: typical number of sessions per week and duration of each session, and progress completing the chats since the previous evaluation. The Investigator or designee will reinforce the key concepts of recovery and working with OXD01 (OXD01 Clinician Guide, Maintaining Motivation and Monitoring Compliance).

## 6. STUDY PROCEDURES

### 6.1 Subject Informed Consent

An ICF approved by the IRB, that includes all of the relevant elements currently required by federal regulations (21 Code of Federal Regulations [CFR] Part 50) and applicable state and local regulations, will be provided to each prospective study subject at screening, before enrollment into the study. The requirements for participation, the type and method of study tests to be administered, any potential or possible hazards, and the subject's right to withdraw from the study at any time will be explained to the subjects by an Investigator or designee. Once an Investigator or designee is assured that an individual candidate understands the implications of participating in this study, the subject will be asked to give consent by signing and dating in the appropriate areas of the ICF. An Investigator or designee will also sign and date the form. A copy of the ICF will be provided to the subject.

The subject's signed and dated informed consent must be obtained before conducting any study specific procedures, including the following:

- Withholding or discontinuation of concomitant medical treatment for the purpose of the study
- Physical examination for the purpose of the study

### 6.2 Remote Visit Procedures

In the *Guidance on Conduct of Clinical Trials of Medical Products during COVID-19 Public Health Emergency Guidance for Industry, Investigators, and Institutional Review Boards* the Food and Drug Administration (FDA) recognizes that the COVID-19 public health emergency may impact the conduct of clinical trials. When circumstances such as quarantines, site closures, and travel limitations lead to difficulties in meeting protocol-specified procedures, sites may use telemedicine to perform procedures or collect endpoint evaluations, with

---

 <https://www.fda.gov/media/136238/download>

the exception of collecting a urine sample for the drug screen. Procedures conducted through telemedicine must be appropriately identified and the circumstance explained in the subject record.

### 6.3 Demographic Data, Medical History

Relevant medical and social history will be documented during the screening visit to assess eligibility.

The following demographic data will be collected:

- Date of birth
- Gender
- Ethnic origin

### 6.4 Opioid Use / Dependence

Opioid use over the past 30 days and the duration of OUD will be documented at screening. The criteria for moderate or severe opioid use disorder according to DSM-V will be verified at screening (Appendix B).

### 6.5 Previous Treatments for Opioid Use Disorder

A treatment history, including counseling, over the previous 2 years for OUD will be recorded at screening.

### 6.6 Concomitant Medications

Concomitant medications will be reviewed at screening, and subjects who require chronic treatment with strong inhibitors or inducers of CYP3A4 will not be eligible for the study (Section 4.3.1).

Medications that are ongoing on study Day 1 will be recorded. Additions, deletions, or changes to concomitant medications after Day 1 will not be recorded.

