**Table 1. Schedule of Events: Screening, Weeks 1-12**

Evaluation	Screening		Treatment									
	Day -21 to 1	Week 1 Day 1	Week 2/3/4 Day 8/15/22	Week 5 Day 29	Week 6 Day 36	Week 7 Day 43	Week 8 Day 50	Week 9 Day 57	Week 10 Day 64	Week 11 Day 71	Week 12 Day 78	
Window	NA	NA	± 1 Day	± 1 Day	± 1 Day	± 1 Day	± 1 Day	± 1 Day	± 1 Day	± 1 Day	± 1 Day	± 1 Day
Informed consent	X											
Demographics	X											
Inclusion/exclusion criteria review	X	X										
Medical history	X											
Opioid use history	X											
Confirm diagnosis - OUD 	X											
Previous treatments for OUD	X											
Concomitant medications 	X	X										
Physical examination	X											
Vital signs	X	X										
Urine drug screen	X	X	X	X	X	X	X	X	X	X	X	X
QFI		X										
TLFB interview – drugs and alcohol		X										
TLFB interview – drugs			X	X	X	X	X	X	X	X	X	X
Review study restrictions with subject	X	X	X	X		X		X		X		
Randomization - IRS 		X										
OXD01 – subject training 		X										
Opioid craving VAS		X		X					X			
QIDS-SR	X											
CGI-S		X										
CGI-I												
Review behavioral health therapies			X	X		X		X		X		X
MAT compliance assessment/counseling			X	X		X		X		X		X
OXD01 compliance assessment/counseling			X	X		X		X		X		X
Adverse Events		X	X	X	X	X	X	X	X	X	X	X

OUD – opioid use disorder; QFI – Quantity-Frequency Index; TLFB – timeline followback method; IRS – interactive response system; MAT – medication-assisted treatment; VAS – visual analog scale; QIDS-SR – Quick Inventory of Depression Symptoms, Self-Report; CGI-S/I – clinical global impression severity/improvement

1. The subject must meet the criteria for moderate or severe opioid use disorder based on DSM-V (Appendix B).
2. Concomitant medications ongoing on Day 1 will be recorded.
3. As soon as the subject is clinically stable on SL BUP/NAL with physical withdrawal symptoms managed, and the subject able to fully participate in OXD01 training, but no greater than 14 days from the first dose of SL BUP/NAL induction.

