#### 4.4 Withdrawal of Subjects

Every subject has the right to refuse participation in the study at any time and for any reason. A subject's participation must therefore be terminated immediately upon his/her request.

An Investigator or the sponsor may withdraw a subject from the study to protect the health of a subject. A subject will be withdrawn from the study for the following safety-related reasons:

- Subject experiences a serious adverse event (SAE) assessed as related to the study treatment by an Investigator or Orexo.

- Subject experiences other unacceptable AE(s) assessed as related to the study treatment by an Investigator.
- Subject requires a prohibited concomitant medication.
- Subject displays hypersensitivity reactions to BUP/NAL.
- Other significant subject safety issue as assessed by an Investigator or Orexo.

An Investigator will make every attempt to explain the reason(s) for discontinuation and to document this in the appropriate sections of the case report forms (CRFs) and in the source documentation, using the following as a guide:

- Subject requests discontinuation.
- Subject is non-compliant, defined as refusal or inability to adhere to the study procedures.
- Treatment failure, as defined by an Investigator, using any and all information including subject interview.
- Unacceptable or intolerable treatment-related AEs.
- Any illness or circumstance that would adversely affect the study procedures or outcome measures.
- At the request of Orexo, regulatory agencies, or institutional review board (IRB).
- Subject is lost to follow-up.

The final record will include reasons for withdrawal, AEs, and any necessary medical treatment.

Subjects who drop out of the study after randomization will not be replaced.

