#### 6.12 Review Study Restrictions

Study restrictions (Section 4.3) will be reviewed with the subject at study screening, and at the visits on Weeks 1-5, 7, 9, 11, 13, 17, and 21.

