## 7.4 Recording of Adverse Events

All AEs should be recorded in the CRFs. Although an AE can initially be acknowledged by anyone in the study team, an Investigator will always be responsible for reporting and assessments of AEs. All AEs should be reported separately (i.e. one record per event). Reporting of AEs are event based, (i.e., an ongoing event will not be closed until resolved or at the end of study). At least the following will be recorded for each AE:

**Description of adverse event:** Adverse event description should be provided in English. Diagnosis is to be preferred over symptoms. If no diagnosis could be made, each symptom will be reported as a separate AE. Abbreviations should be avoided. Descriptive words should be used for ongoing conditions as applicable (e.g. "exacerbation of herpes genitalis", "worsening of eczema" etc.).

**Serious adverse event:** Yes or no (definition of SAE in section 7.1.4). If Yes, an SAE Report Form needs to be completed.

**Maximum intensity:** Maximum intensity of the AE during the complete course of the event should be recorded in accordance with the following definitions:

- Mild – Awareness of sign and symptoms but easily tolerated
- Moderate – Discomfort sufficient to cause interference with normal activities
- Severe – Incapacitating, with inability to perform normal activities

**Duration:** The duration of the AE will be recorded by start and stop date and time.

**Relatedness to medical device (causality):** Relatedness to the medical device will be assessed by an Investigator according to the below categories.

- *Not related:* A causal relationship between the medical device and the AE is assessed as not possible (e.g. due to onset in relation to use of the device or that another cause of the AE has been identified)
- *Related:* A causal relationship between the medical device and the AE is assessed as at least possible

**Actions taken:** Actions taken in relation to the AE with respect to use of the medical device, should be recorded as:

- Use of the medical device withdrawn
- Use of the medical device interrupted
- Use of the medical device is reduced
- Use of the medical device is increased
- Use of the medical device not changed
- Not applicable
- Unknown

Any medication given to treat the AE will be recorded separately on the concomitant medication list of the CRFs.

**Outcome:** The outcome of the AE should be recorded.

- Recovered/Resolved
- Recovering/Resolving

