Concomitant medications will be coded to anatomical therapeutic chemical (ATC) class and preferred term using the WHO Drug Dictionary version March 2021G B3. For summary purposes, medications will be considered prior medications if they stopped prior to the first use of study device (Day 1) and concomitant medications if they were taken at any time after the first use of study device (i.e. started prior to Day 1 and were ongoing or started after Day 1).

If a medication has incomplete start or stop dates, dates will be imputed to determine whether a medication should be considered prior or concomitant. If a medication start date is incomplete, the first day of the month will be imputed for missing day and January will be imputed for

missing month. If a medication stop date is incomplete, the last day of the month will be imputed for missing day and December will be imputed for missing month. Incomplete start and stop dates will be listed as collected without imputation.

Counts and percentages of subjects taking concomitant medications by ATC class and a preferred term will be summarized by treatment based on the Safety Population.

3.3.8 *Study Device Compliance*

Dosing instructions will be reviewed and subjects will be interviewed to assess treatment compliance at the following Visits: Weeks 2-5, 7, 9, 11, 13, 17, 21, and 25.

Percent compliance of study device OXD01 will be calculated as the number of OXD01 sessions taken / the number of expected OXD01 sessions taken. Percent compliance to the study device regimen will be summarized based on the Safety Population with descriptive statistics and with counts and percentages of subjects with compliance in the following categories:

- <50%
- 50-80%
- 80-100%
- >100%

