3.4 Efficacy Assessment

Efficacy data will be summarized by randomized treatment based on the FA Population. The primary efficacy endpoint will also be summarized based on the mFA Population.

3.4.1 *Primary Endpoints Analysis*

The primary objective of the study is to determine whether the combination of SL BUP/NAL SOC background therapy and the digital therapeutic OXD01 is superior to SL BUP/NAL alone to reduce opioid use, as measured by the treatment success rate. Treatment success is defined as the subject having $\geq 80\%$ of urine drug tests negative for opioids plus $\geq 80\%$ of self-reports negative for illicit opioid use (from the TLFB interview at the same visit) from Week 6 to Week 25. Each subject will be evaluated as a success or failure for this metric and the proportion of subjects in each group demonstrating $\geq 80\%$ of urine drug tests negative for opioids plus negative self-reports for illicit opioid use (from the TLFB interview) will be tested using chi-squared test. Count and percentage of the subjects with treatment success will be summarized by treatment based on FA Population.

If the subject withdrew the study, then the urine drug tests for opioids and self-reports for illicit opioid use after withdrawal will be imputed as positive. If the subject completed the study with any missing visit, then the urine drug tests for opioids and self-reports for illicit opioid use for the missing visit will be imputed as positive.

Sensitivity analysis 1

As supportive analyses to the primary analysis for the primary endpoint, sub-group analysis using a similar chi-squared test as described above will be repeated for the following factors:

- Percentage of subjects meeting primary endpoint by reported compliance rate or who achieved greater than 80% completion of the visits during Week 6 to Week 25
- Subjects who took the dose of buprenorphine versus retention.
 - Target dose or lower: ≤ 16 mg buprenorphine for Suboxone or equivalent formulation; or ≤ 11.4 mg Zubsolv
 - Higher dose than target dose: > 16 mg buprenorphine for Suboxone or equivalent formulation; or > 11.4 mg Zubsolv
- Subjects who received additional behavioral health services

Sensitivity analysis 2

As supportive analyses, the primary endpoint and key secondary endpoints will be performed using the similar statistical methods based on mFA Population.

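### Medication changes after Day 1 are not to be recorded, yet the adverse-event section and the SAP's own definition need them, and the buprenorphine-dose split has no stated time point or data source

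*Protocol*

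**What the plan says.** Three places agree that recording stops at Day 1. Protocol 6.6 says "Additions, deletions, or changes to concomitant medications after Day 1 will not be recorded". Footnote 2 to the schedule of events (Protocol Table 1) says "Concomitant medications ongoing on Day 1 will be recorded", and the schedule marks this item at screening and Day 1 only. SAP 3.3.7 opens by restating the 6.6 rule.

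Two places assume later recording:
- Protocol 7.4: "Any medication given to treat the AE will be recorded separately on the concomitant medication list of the CRFs".
- SAP 3.3.7, in its summary rules, classes drugs as "concomitant medications if they were taken at any time after the first use of study device", explained in brackets as "i.e. started prior to Day 1 and were ongoing or started after Day 1".

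SAP 3.4.1, under Sensitivity analysis 1, lists a subgroup described as "Subjects who took the dose of buprenorphine versus retention". It is cut at 16 mg of buprenorphine for Suboxone or equivalent, or 11.4 mg for Zubsolv. Protocol 5.2 has the Investigator directing daily dosing from Day 1 to Day 169. Protocol 5.2.1 has compliance interviews at 11 visits but does not say that the dose is recorded.

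SAP Section 6 says the SAP does not deviate from version 1.0 of the protocol.

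**The concern.** A site that treats an adverse event in, say, Week 10 is told by one section to log the drug and by another not to. Sites will resolve this differently, so the concomitant medication table would mix Day 1 medications with a site-dependent sample of later ones, under a definition that promises all of them.

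The dose subgroup has a related weakness. Day 1 falls no more than 14 days after the first induction dose, and about 24 weeks of Investigator-directed dosing follow. Without a stated time point, two analysts could use the Day 1, last, highest or average dose and classify subjects differently. Any dose taken after Day 1 can also be influenced by the assigned arm and by early response, so a split on it would not compare randomized groups like with like.

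There is a smaller issue for the primary endpoint. The documents do not say how an opioid prescribed during follow-up is identified or classified.

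**Working it through.** **1. The recording rules side by side.** Adverse events are collected on Day 1 and at all 24 visits from Week 2 to Week 25 (25 − 2 + 1 = 24). Concomitant medications are marked at none of those 24. A drug first given for an event after Day 1 is therefore required by Protocol 7.4 and barred by Protocol 6.6. In SAP 3.3.7 the definition has two parts: ongoing at Day 1, and started after Day 1. Only the first can be filled under the rule stated in the same section. The table can still be run, but it will not contain what its definition says.

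**2. The dose split.** SAP 3.4.1 gives cut-offs but no time point and no data source. The documents do not say whether buprenorphine/naloxone, as background therapy, falls under the 6.6 rule. A Day 1 dose could be captured as an ongoing medication; no section says later doses are captured. Only a change that crosses the 16 mg or 11.4 mg cut-off would alter a subject's category.

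**3. Prescribed opioids and the primary endpoint.** The urine component counts opioids from any source. The self-report component is worded as illicit use, but the timeline followback is a Yes/No question (Protocol 6.11), and its instructions (Appendices D and E) list opiates with prescription products as examples, without asking about source. A truthful report of a prescribed opioid would count as positive.

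Weeks 6 to 25 give 25 − 6 + 1 = 20 visits. Success needs 0.80 × 20 = 16 negative, so 4 may be positive or missing, since SAP 3.4.1 imputes missing as positive. Assume visits are independent, each negative with probability q (not given in the documents). If k visits are made positive by a prescribed opioid, the chance of success is P(X ≥ 16) with X ~ Binomial(20 − k, q):

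| q | k = 0 | k = 1 | k = 2 |
|---|---|---|---|
| 0.85 | 83.0% | 68.4% | 48.0% |
| 0.90 | 95.7% | 88.5% | 73.4% |
| 0.95 | 99.7% | 98.7% | 94.2% |
| 1.00 | 100% | 100% | 100% |

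A subject who is otherwise clean loses nothing from one or two such visits. One near the threshold can lose a good deal.

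**4. Trial-level scale.** First the plan's own figure. With p1 = 0.12, p2 = 0.25, two-sided α = 0.05 and 90% power, n = [1.960·√(2p̄(1−p̄)) + 1.282·√(p1(1−p1) + p2(1−p2))]² / (p2−p1)², where p̄ = 0.185. This gives 186 per arm, or 201 with continuity correction, which reproduces the stated figure of about 200. Medication recording does not enter it.

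Now assume that a fraction m of true successes in both arms is scored as failure because of prescribed opioids. The rates become (1−m)·0.12 and (1−m)·0.25. Power at 200 per arm is Φ{[(p2−p1)√200 − 1.960√(2p̄(1−p̄))] / √(p1(1−p1) + p2(1−p2))}:

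| m | 0 | 2% | 5% | 10% | 20% |
|---|---|---|---|---|---|
| Power | 0.920 | 0.914 | 0.904 | 0.884 | 0.836 |

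The documents give no value for m.

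**The case against.** The Day 1 limit appears in Protocol 6.6, the schedule footnote and the SAP, so it looks deliberate, and it is defensible for a device added to standard-of-care medication. That stands as a reason not to ask for full medication logging. It does not remove the conflict with Protocol 7.4 or with the SAP's own definition.

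Three stronger readings are tempting, and the documents do not support them.

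- *The withdrawal rule cannot work.* Protocol 4.4 withdraws a subject when "Subject requires a prohibited concomitant medication", and one might infer that this needs a medication log. It does not. Protocol 6.12 says "Study restrictions (Section 4.3) will be reviewed with the subject at study screening" and again at Weeks 1–5, 7, 9, 11, 13, 17 and 21. Withdrawal reasons are documented, and SAP 3.3.2 tabulates major deviations. What is missing is a way to verify adherence from a medication record.
- *The dose analysis rests on the Day 1 dose alone and misclassifies everyone whose dose changes.* No section puts buprenorphine/naloxone under the 6.6 rule, the Investigator prescribes it, and only changes across the cut-off matter. The defect is an unstated source and time point.
- *The primary endpoint is undermined.* The urine component is defined on any opioid and is computable as written. Protocol 4.2 excludes subjects who need chronic opioid treatment or have unremitting or unstable chronic pain. An opioid given for an adverse event would be logged if 7.4 is followed. Nothing suggests that prescribed opioids differ between arms.

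**Conclusion.** The contradiction is on the face of the documents and should be corrected: the rule in Protocol 6.6, the schedule footnote and SAP 3.3.7 cannot be followed together with Protocol 7.4, and the SAP's concomitant medication table will omit part of its own definition. The number of adverse-event treatments affected cannot be estimated from the documents. The dose subgroup is under-specified in time point and source.

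The primary analysis is not invalidated. The handling of prescribed opioids is a gap in classification with a likely modest effect. That judgement rests on the four-visit allowance and on assumed loss fractions: power stays above 0.90 up to a 5% loss and reaches 0.884 at 10%. Missing visits draw on the same allowance, so the cushion is smaller for subjects who also miss visits.

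**What to change.** 1. Reconcile Protocol 6.6, the schedule footnote and the opening of SAP 3.3.7 with Protocol 7.4 and the SAP definition. Suggested rule: after Day 1, sites record adverse-event treatments, any medication named in Section 4.3.1, opioids given under medical care, and buprenorphine/naloxone dose and dose changes. This concerns recording only and changes no clinical rule.
2. SAP 3.2.2 shows that subjects are already enrolled, so some of these data may be lost. Where they are, limit the SAP 3.3.7 definition to medications ongoing on Day 1, say so in the table title, and list the change in SAP Section 6. Because the Investigator prescribes buprenorphine/naloxone, dose history may be recoverable from site prescribing records.
3. In SAP 3.4.1, name the data source and use the Day 1 dose for the subgroup test. Report later dose changes by arm descriptively, since later dose is a post-randomization variable.
4. Optionally, add a supportive analysis in which a visit is not counted as illicit opioid use when the positive urine and any reported opiate use are both explained by a documented prescription. Requiring a negative self-report instead would not work, because the timeline followback does not ask about source. Leave the primary analysis unchanged.

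The cost is a protocol clarification, a short CRF page at visits already held, and a little more site data entry. The SAP edits can be made before database lock.
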